- **Surgical Success Primary Endpoint:** The primary effectiveness endpoint is the surgical success rate, defined as the procedure not going into conversion. Conversion is defined as the switch from a robotic-assisted approach using the Hugo system to a robotic-assisted approach utilizing an FDA cleared robotic-assisted device, laparoscopic or open surgery.
- **Sample size and enrollment proportions:** The effectiveness endpoint sample size of up to 141, is based on the rationale of an acceptable surgical success rate of 90% or higher, a power of 80% or higher, and a performance goal of 85%.

The hypothesis will be tested using the Clopper-Pearson exact method at one-sided alpha of 0.025.

- **Follow-up timeframe:** Surgical success will be assessed at the index procedure.

Additional specific design justifications were also considered while developing this clinical investigation of the intended use.

- **Subject Selection:** Excluding subjects with high-risk comorbidities affecting their surgical eligibility will minimize the risk to subjects. Restricting enrollment to subjects with a life expectancy of 6 months or more is intended to provide a greater follow-up rate on the primary endpoint.
- **Study Procedures:** The study procedures chosen (partial or radical nephrectomy, radical prostatectomy, and radical cystectomy) are representative, in terms of technical difficulty, of

most surgical procedures in urology. They are also the highest-volume urology oncologic surgeries.⁴ Since the safety profiles or major complication rates are very different among the three surgeries, a separate performance goal is pre-specified for each of the three surgery types (as per FDA recommendation). The performance goals are determined based on published data from the literature search.

- **Number of Study Sites:** Up to 6 study sites with up to 15 surgeons are planned in order to ensure generalizability of the data and account for the expected low volume of subjects undergoing radical cystectomy. The sponsor reserves the right to halt enrollment at any individual site for any individual procedure type to ensure a balanced enrollment and avoid the introduction of bias.

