14.4.1 Primary Objective #1 (Effectiveness)

The primary effectiveness objective of this study is to confirm that the Medtronic Hugo™ RAS System is effective when used for urologic robotic assisted surgery. The primary effectiveness endpoint is the surgical success rate, as defined in **Section 6.4.2**.

The primary effectiveness hypothesis is to test if the surgical success rate is above the performance goal. Based on published data and clinical practice, a surgical success rate of 90% or higher is expected. A performance goal of 85% (based on the literature) is pre-defined to evaluate the surgical success rate. Let P be the surgical success rate in this study. The statistical hypothesis is formulated as follows:

$$H_0: P \leq 85\% \text{ vs. } H_a: P > 85\%$$

The hypothesis will be tested using the Clopper-Pearson exact method at one-sided alpha of 0.025.

Performance Goal Rationale and Sample Size

Analyses were performed based on available literature. Point estimates along with 95% and 99% predicted intervals were calculated to provide plausible range of potential effect size. Clinically meaningful margins and statistical precisions have been taken into account to determine the appropriate performance goals. The calculation details and rationales are summarized in the following table.

Surgery Type	PG	Sample Size	Rationale
Nephrectomy	85%	141	The mean effect size for conversions is 0.022 with a 95% confidence interval of 0.017 to 0.029. The 95% prediction interval is 0.005 to 0.098. The 99% prediction interval is 0.003 to 0.153. A performance goal of 85% for surgical success rate was set, which is equivalent to 0.15 as the conversion rate (1-success rate), aligned with the 95% to 99% of predictive intervals upper limit of 0.098 to 0.153. A single-group design will be used to test whether the proportion is greater than 0.85 ($H_0: P \leq 0.85$ versus $H_a: P > 0.85$). The comparison will be made using a one-sided, one-sample exact test, with a target Type I error rate (α) of 0.025. To detect a difference ($P_1 - P_0$) of 0.102 with a sample size of 126, which accounts for 10% attrition from the overall study sample size of up to 141, the power is 0.96.
Prostatectomy			
Cystectomy			

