14.7 Sample Size Determination

The sample size for the study was estimated based on the primary safety and effectiveness hypotheses.

Power calculation was performed using statistical software NCSS PASS 2023.

The effectiveness hypothesis is to test if the surgical success rate is above the performance goal. The surgical success rate is expected to be 90% or higher. A performance goal is set to be 85%. A sample size of 126 subjects will provide more than 80% power at one-sided alpha of 0.025 (with an expected rate of 95.2% or higher in this study).

Safety is also considered for sample size determination. The primary safety endpoint is the major complication rate. A statistical hypothesis with a performance goal is specified for each of the three surgery types. The performance goals are determined based on analyses of published literature by taking into account clinically meaningful margins and statistical precisions. Each individual hypothesis is adequately powered with at least 80% power at a one-sided alpha level of 0.008 with multiplicity adjustment taken into consideration. The sample sizes for the three surgery types are up to 55, up to 55 and up to 31 for Nephrectomy, Prostatectomy and Cystectomy respectively, after taking 10% attrition into account (up to 141 subjects in total).

With the consideration of both effectiveness and safety, a total of up to 141 subjects are planned to be treated in this study. Up to six study sites will be used. To keep enrollment balance, each study site will be allowed to enroll no more than 30% of the total population.

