The effectiveness hypothesis is to test if the surgical success rate is above the performance goal. The surgical success rate is expected to be 90% or higher. The effectiveness performance goal is set to be 85%. A sample size of 126 subjects will provide more than 80% power at one-sided alpha of 0.025 (with an expected rate of 95.2% or higher in this study).

Safety was also considered for the sample size determination. The primary safety endpoint is major complication rate. A statistical hypothesis with a performance goal is specified for each of the three urologic procedures (nephrectomy, prostatectomy, cystectomy). The safety performance goals were determined based on analyses of published literature by taking into account clinically meaningful margins and statistical precisions. Each individual hypothesis was adequately powered with at least 80% power at an alpha level of 0.008 with multiplicity adjustment taken into consideration. The sample sizes for the three surgery types are up to: 55, 55, and 31 for nephrectomy, prostatectomy, and cystectomy, respectively. After taking 10% attrition into account the total number of subjects planned for this study based on the sample size calculations was up to 141 subjects. Full calculations for the safety sample sizes and the associated power for each urologic procedure are below.

Nephrectomy: The mean effect size is 0.029 with a 95% confidence interval of 0.022 to 0.038. The 95% prediction interval is 0.017 to 0.047. The 99% prediction interval is 0.014 to 0.058. A performance goal of 0.20, while greater than the predicted interval, broadly aligns with the upper limits for each nephrectomy study with a comparable study size (95% upper limits ranging from 0.100 to 0.539) and is clinically appropriate. A performance goal of 0.20, assuming a sample size of up to 55 (with 10% attrition n=49), one-sided alpha of 0.008 (Bonferroni Correction), and mean effect size of 0.029, results in a power of 95%.

Prostatectomy: The mean effect size is 0.029 with a 95% confidence interval of 0.016 to 0.051. The 95% prediction interval is 0.004 to 0.173. The 99% prediction interval is 0.002 to 0.316. A performance goal of 0.20 (20%), is clinically appropriate. A performance goal of 0.20, assuming a sample size of up to 55 (with 10% attrition n=49), one-sided alpha of 0.008 (Bonferroni Correction), and mean effect size of 0.029, results in a power of 95%.

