7.9.1.1 Hypothesis

The primary effectiveness hypothesis is to test if the surgical success rate is above the performance goal. Based on the Clinical Data Analysis of Robotic-Assisted Surgical Procedures in Urology Rev B (Medtronic on file), henceforth referred to as the Urology Clinical Data Analysis and clinical practice, a surgical success rate of 90% or higher is expected. To account for natural variability between sites, surgeons, and surgery types an overall performance goal of 85% (based on the literature) is pre-defined to evaluate the surgical success rate. Let P be the surgical success rate in this study. The statistical hypothesis is as follows:

$$H_0: P \leq 85\% \quad \text{vs.} \quad H_a: P > 85\%$$

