7.9.1.4 Rational for Performance Criteria

Analyses were performed based on available literature. Point estimates along with 95% and 99% predicted intervals were calculated to provide plausible ranges of potential effect sizes. Clinically meaningful margins and statistical precisions have been taken into account to determine the appropriate performance goals.

The mean effect size for conversions is 0.024 with a 95% confidence interval of 0.019 to 0.032. The 95% prediction interval is 0.004 to 0.125. The 99% prediction interval is 0.003 to 0.20. A performance goal of 85% for surgical success rate was set, which is equivalent to 0.15 as the conversion rate (1-success rate), aligned with the 95% to 99% of predictive intervals upper limit of 0.125 to 0.2. A single-group design will be used to test whether the proportion is greater than 0.85 ($H_0: P \leq 0.85$ vs. $H_1: P > 0.85$).

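### Protocol 6.4.2 bases the effectiveness sample size on 90% success with 80% power, but the exact test has only 27–39% power at 90%; the power calculation uses 95.2%

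*Protocol*

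**What the plan says.** Protocol Section 6.4.2, under Effectiveness, gives the basis for up to 141 subjects as "the rationale of an acceptable surgical success rate of 90% or higher, a power of 80% or higher, and a performance goal of 85"%. It then fixes the test as Clopper-Pearson exact at one-sided alpha 0.025. The rate 95.2% does not appear there. The statistics entry of the synopsis (Protocol Section 3) also claims more than 80% power against 85% and names no alternative rate.

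The calculation is in Protocol 14.4.1. Its rationale table takes a difference of 0.102 above 0.85 (that is, 95.2%) with 126 subjects, "which accounts for 10% attrition from the overall study sample size of up to 141, the power is 0.96". Protocol 14.7 and SAP Section 6 attach the claim of more than 80% power to 126 subjects "with an expected rate of 95.2% or higher in this study".

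The same sections also present 90% as the expectation:

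- Protocol 14.4.1: "Based on published data and clinical practice, a surgical success rate of 90% or higher is expected".
- Protocol 14.7: "The surgical success rate is expected to be 90% or higher". SAP Section 6 says the same.
- SAP 7.9.1.1 bases it on the sponsor's on-file analysis: "Urology Clinical Data Analysis and clinical practice, a surgical success rate of 90% or higher is expected".

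The literature summaries point higher still. SAP 7.9.1.4 reports "The mean effect size for conversions is 0.024 with a 95% confidence interval of 0.019 to 0.032", and the Protocol 14.4.1 table gives a mean conversion rate of 0.022.

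**The concern.** Section 6.4.2 supplies every part of a power statement: null rate, alternative, power, test and alpha. A reader will take it that the test has at least 80% power if the device performs at the rate called acceptable. If that is not so, a failed effectiveness test at a true rate of 90% would look like an unlikely accident when it is in fact the most probable result.

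There is also a consistency problem. Protocol 14.7 and SAP Section 6 each give two expected rates, 90% or higher and 95.2% or higher, in nearby sentences without saying how they relate. The 90% is attributed to published data or to the sponsor's analysis. No source is stated for 95.2%, the rate on which the power depends.

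**Working it through.** **Inputs**

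- Null success rate (goal): 0.85 (Protocol 6.4.2, 14.4.1, 14.7).
- Test: exact binomial, one-sided alpha 0.025 (Protocol 6.4.2, 14.4.1).
- Evaluable subjects: 126 after 10% attrition (141 × 0.9 = 126.9, taken as 126), up to 141 with none.
- Alternatives: 0.90 (Protocol 6.4.2); 0.952 (0.85 + 0.102, Protocol 14.4.1); 0.976 and 0.978 (1 − 0.024 from SAP 7.9.1.4; 1 − 0.022 from Protocol 14.4.1).

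**Formulas**

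Critical count c = smallest x with P(X ≥ x | n, 0.85) ≤ 0.025.
Power at true rate p = P(X ≥ c | n, p).

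**Step 1: reproduce the plan's figure.** For n = 126, c = 116 with exact size 0.0131. Power at 0.952 is 0.9595, which matches the stated 0.96.

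**Step 2: power at the rate named in 6.4.2**

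| n | c | c/n | exact size | power at 0.90 | power at 0.952 |
|---|---|---|---|---|---|
| 126 | 116 | 92.1% | 0.0131 | 27.5% | 96.0% |
| 127 | 116 | 91.3% | 0.0245 | 37.5% | 98.1% |
| 136 | 124 | 91.2% | 0.0233 | 39.0% | 98.6% |
| 141 | 129 | 91.5% | 0.0157 | 33.8% | 98.1% |

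Over every n from 126 to 141, power at 0.90 is lowest at n = 126 (27.5%) and highest at n = 136 (39.0%). It moves up and down because the test is discrete. The chance of failing at a true 90% is therefore 61% to 73% (1 − 0.390 to 1 − 0.275).

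**Step 3: observed rate needed to pass.** The smallest passing proportion lies between 91.2% (124/136) and 92.1% (116/126). An observed 90% does not pass at any n in the range. For example, 0.9 × 126 = 113.4 against 116 needed, and 0.9 × 141 = 126.9 against 129 needed.

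**Step 4: true rate that gives 80% power.** About 93.5% at n = 126, 92.7% at n = 136 (the lowest) and 92.9% at n = 141.

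**Step 5: power at the literature-implied rates.** At 97.6% and 97.8% it exceeds 99.9% throughout the range (for example 0.99975 and 0.99988 at n = 126).

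**Step 6: does another method rescue 80% at 90%?**

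| Method | n = 126 | n = 141 |
|---|---|---|
| Exact, one-sided 0.05 | 50.4% | 44.8% |
| Normal, null variance, 0.025 | 32.2% | 36.2% |
| Normal, continuity-corrected, 0.025 | 27.1% | 31.1% |
| Normal, variance at the alternative, 0.025 | 46.5% | 50.8% |
| Normal, variance at the alternative, 0.05 | 58.9% | 63.1% |

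None does. For scale only, the exact test at 0.025 first reaches 80% power at a true 90% with 356 evaluable subjects and stays there from 379.

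**The case against.** The best defence is that no calculation is wrong. The one effectiveness power figure in the documents, 0.96, is correct, and the sections that govern the analysis tie the power to 95.2%. Section 6.4.2 speaks of an acceptable rate of at least 90% and power of at least 80%; 95.2% and 96% satisfy both inequalities, and an acceptable rate need not be the planning rate. The source of 95.2% may lie in the on-file analysis cited in SAP 7.9.1.1. The 39% is a peak at n = 136, which is not a planned size. Low power at 90% lowers the sponsor's chance of success but does not make a false pass more likely.

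Much of this stands. The 0.96 is right, only 6.4.2 pairs 90% with 80% power, and the elsewhere-stated expectation of 90% or higher does not strictly contradict 95.2%. The planning rate is also conservative against the literature means.

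The reading by inequalities does not save 6.4.2. When a range of alternatives is given as the basis for a sample size, its lower end must deliver the stated power. Here that end delivers about a third to a half of it (27.5/80 to 39.0/80), and the rate that does deliver it is missing from the section. At 126 and 141 alone the power is 27.5% and 33.8%, so the conclusion does not depend on the peak.

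**Conclusion.** The concern holds. As written, the rationale in 6.4.2 claims power that the design does not have: 27.5% to 39.0% at a true 90%, against 80% stated. At the rate actually used, 95.2%, power is 96.0% with 126 subjects and 98.1% with 141, so the sample size is adequate for that alternative.

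This rests on the exact one-sided 0.025 test against 85% and on 126 to 141 evaluable subjects, all taken from the documents. The defect is confined to the stated justification and to the unreconciled expected rates. Enrolment, the test, the goal, type I error and the decision rule are unaffected. It should be fixed, but it does not threaten the validity of the analysis.

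**What to change.** **Essential, Protocol 6.4.2:** name 95.2% as the powered alternative (96% power with 126 evaluable subjects, one-sided 0.025, goal 85%) and remove 90% as the basis for the power claim.

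**Advisable alongside it:**

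- In Protocol 14.4.1 and 14.7 and SAP Section 6 and 7.9.1.1, say how the two rates relate, for example 90% as the acceptable floor and 95.2% as the planning rate.
- Give the source of 95.2%, and note that it is below the 97.6% to 97.8% implied by the literature conversion means.
- Add one sentence: power is about 27% to 39% if the true rate is 90%, and 80% power needs a true rate of about 93.5% with 126 subjects or about 93% with 141.

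The cost is wording in the protocol and SAP. No increase in enrolment is proposed. The plan gives up the 80% claim at 90% and discloses the low power there.

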7.1 General

The Medtronic Hugo™ RAS System is a modular robotic platform for performing robotically assisted minimally invasive surgery. It enables the surgeon, sitting at an ergonomically adjustable console, to view the surgical field in three dimensions (3D) and control movements of the endoscope and instruments with individual robotic arms at the operating table. It also allows surgeons and operating room (OR) teams to manually control arms at the bedside, including using one arm as an endoscope holder. The Medtronic Hugo™ RAS System platform supports a portfolio of wristed instruments.

There are no anticipated changes to the Medtronic Hugo™ RAS System during the course of the investigation.

Figure 1: Medtronic RAS Overview -- Left to Right: System Tower, Surgeon Console, Arm Carts (4)

The main components of the Medtronic Hugo™ RAS System are described in the following subsections.

7.1.1 Hugo™ RAS Surgeon Console

The surgeon console is an open console that consists of a large flat screen with a high-definition 3D passive display, a small touchscreen interactive display, adjustable ergonomic controls, an armrest, two surgeon hand controllers, a set of foot pedals, and 3D surgeon and observer glasses. Sensors in the

Medtronic Business Restricted

This document is electronically controlled

CONFIDENTIAL 056-F275 Rev E Clinical Investigation Plan Template

surgeon console track the movement of the 3D glasses worn by the surgeon and can clutch movement of the instruments if the surgeon looks away from the 3D display. The surgeon hand controllers are easy to move and respond to wrist movement.

7.1.2 Hugo™ RAS Arm Cart Assembly

The arm carts consist of movable platforms with casters, each supporting a modular and extendable arm. Up to four arm carts can be connected to the system tower for simultaneous use during RAS. The arm carts are portable and easily movable within the operating room and the hospital. Prior to surgery, the OR team positions the arm carts around the surgical table according to the surgical procedure. The team can adjust the arm carts and arms to accommodate subject positioning and optimize bedside access to the subject.

7.1.3 Hugo™ RAS Tower, 120v

The system tower houses computers, the endoscope system, the electrosurgical generator, the power management system with a backup battery, and the high-definition OR team touchscreen interactive display. The system tower allows the surgeon console to control the movements of up to four arms. It may also be used without the surgeon console to power up to four arms for standalone manual control at the bedside, or by itself for standard laparoscopic visualization and electrosurgery.

7.1.4 Hugo™ RAS Endoscope Adapter

The Hugo™ RAS endoscope adapter is intended to hold the compatible Karl Storz TIPCAM ®1 S 3D endoscope used with the Medtronic Hugo™ RAS System. The endoscope adapter will be attached to the robotic arm for the Medtronic Hugo™ RAS System during the representative surgical procedures set forth in the Medtronic Hugo™ RAS System user guide.

7.1.5 Hugo™ RAS Sterile Interface Module

The Hugo™ RAS sterile interface module device is intended to be used with the Hugo™ RAS system as a universal connection on the robotic arm for the Hugo™ RAS sterile instruments and endoscope adapter during the representative surgical procedures set forth in the Hugo™ RAS system user guide.

7.1.6 Hugo™ RAS Arm Cart Sterile Drapes

The Hugo™ RAS Arm Cart Sterile Drape is a single use, sterile drape that is designed as part of the Hugo™ RAS System. There are three types of sterile drapes, and each is designed to cover a different non-sterile section of the Hugo™ RAS Arm Cart. The Arm Cart Sterile Drape covers the non-sterile robotic arm, or upper part of the arm cart, or lower part of the arm cart of the Hugo™ RAS System in order to allow the system to be used within the sterile field.

For Hugo™ RAS System configuration information, Instructions for Use, indications, contraindications, warnings, and precautions, refer to the User Guide for the Hugo™ RAS System.

The product is to be used by medical professionals qualified in the transportation, preparation, and use of surgical devices. The Hugo™ RAS System is intended for use in a sterile operating room environment.

7.1.7 Wristed Instruments

The Hugo™ RAS system's wristed instruments are minimally invasive instruments that provide two degrees of freedom (pitch, yaw) at the distal end of the instrument in addition to the opening and closing of the instrument jaws. These degrees of freedom, when commanded from the surgeon console, allow for precise and dexterous control of the instrument by the surgeon. Hugo™ RAS system configuration information, Instructions for Use, indications, contraindications, warnings, and precautions, refer to the Hugo™ RAS system user guide.

These products are to be used by medical professionals qualified in the transportation, preparation, and use of surgical devices.

The Hugo™ RAS system is intended for use in a sterile operating room environment.

7.1.7.1 Hugo™ RAS Monopolar Curved Shears

The Hugo™ RAS Monopolar Curved Shears is a Hugo™ RAS wristed instrument with a sharp curved cutting-blade end effector for tissue manipulation including blunt dissection, sharp dissection, electrocautery and cutting. The Hugo™ RAS monopolar tip cover is required when using the Hugo™ RAS monopolar curved shears.

7.1.7.2 Hugo™ RAS Monopolar Tip Cover

Monopolar shears are used to cut and cauterize tissue, however only the jaws should be energized. A tip cover is installed over the distal end of the instrument to prevent other metallic parts of the distal end from conducting electricity. This cover should be checked for structural integrity after every instrument extraction to prevent unintended burns to the subject as outlined in the Instructions for Use.

7.1.7.3 Hugo™ RAS Bipolar Fenestrated Grasper

The Hugo™ RAS Bipolar Fenestrated Grasper is a Hugo™ RAS wristed instrument with a fenestrated jaw end effector for tissue manipulation including grasping, blunt dissection, approximation, electrocautery, and suturing.

7.1.7.4 Hugo™ RAS Bipolar Maryland Forceps

The Hugo™ RAS Bipolar Maryland Forceps is a Hugo™ RAS wristed instrument with a curved tapered jaw end effector with fenestration at the base of the jaw for tissue manipulation including grasping, blunt dissection, approximation, electrocautery, and suturing.

